between the sucralose groups versus placebo will be compared, adjusting for BMI. In the case of chronic exposure to the sweetener, the AUC values between the sucralose groups versus placebo will be compared after 10 weeks, and the AUC values will be compared at the beginning and end of the study in the group that received sucralose, adjusting in both cases for BMI. In addition to the determination of glucose levels during the two CTOGs, the circulating levels of insulin, glucagon, C peptide, GIP, GLP-1, TNF- α , pCr, IFN- γ , IL-1 β , IL-4, IL-6, IL-10, IL-12, IL-13, IL-17, IL-23, and inflammatory monocytes CD14hiCD16 + CD11c + CCR2hiCX3CR1lowCD206-, with the purpose of comparing their values in the acute exposure scheme and chronic to sucralose, adjusting for BMI. The samples of excrement from acute and chronic exposure will be processed to extract the DNA and run them in PCR in real time and the percentage of each bacteria present in feces will be compared at the beginning and at the end. The difference between the two samples will be analyzed by means of square chi.

Ethical considerations

This study will be carried out in compliance with the guidelines of the protocol, with the ethical principles of the Declaration of Helsinki in its most recent version approved during the 64th Assembly of the World Association of Physicians, in Fortaleza Brazil, in October 2013, in accordance to the principles that govern human research in the General Health Law and in accordance with the ethical and research guidelines of the General Hospital of Mexico "[name].

REFERENCES

3. Garcia LM, da Silva KS, Del Duca GF, da Costa FF, Nahas MV. Sedentary behaviors, leisure-time physical inactivity, and chronic diseases in Brazilian workers: a cross sectional study. *J Phys Act Health.* 2014;11(8):1622-34.

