Statistical Analysis Plan

México CDMX. January 20th 2016

Effect of Acute or Chronic Ingestion of Sucralose on Serum Insulin in Young and Healthy Adults: A Randomized, Double-Blind, Placebo-Controlled Trial.

The statistical analysis will help us to provide accurate and quantifiable data in order to increase the documented information about the sucralose; this analysis will also help us to have a better reliability on the study results.

Estimation of sample size

Considering the results on the difference of the averages of the areas under the curve for plasma insulin in obese volunteers exposed to sucralose and water, before an oral glucose load, as reported by Pepino et al., [1], the estimation of the Sample size was:

t tests - Means: Difference between two independent means (two groups)

Analysis: A priori: Compute required sample size

Input:

Tail(s)	=	One
Effect size d	=	0.419231264
α err prob	=	0.05
Power (1- β err prob)	=	0.8
Allocation ratio N2/N1	=	1

Output:

Noncentrality parameter δ	=	2.5153876
Critical t	=	1.6556552
Df	=	142
Sample size group 1	=	72
Sample size group 2	=	72
Total sample size	=	144
Actual power	=	0.8046976

For the estimation of the sample size the program GPower version 3.1.9.2 (University of Düsseldorf, Germany) was used. The difference between two

averages was estimated by means of a test of t, of an address, with an alpha value (0.05), assuming unequal variances, for a power of proof of 80%, a value of Cohen of 0.419231264, the sample size is 72 volunteers per group, the total sample size is left in 144 volunteers.

The demographic analysis will be assessed with descriptive statistics, ensuring the two groups are balanced in their moments for the main variables.

The statistical analysis of the presence or occurrence of any inflammatory process during the the study will be carried out by comparing the before / after differences between the sucralose and water groups for the whole sample, adjusting for BMI, these differences will be compared for each analyte related to chronic inflammation such as C-reactive protein, tumor necrosis factor-alpha, interleukin (IL) 6, IL-12, IL-10 and inflammatory monocytes CD11c + CCR2High.

In order to calculate the area under the glucose tolerance test curve will be assessed using the trapezium method [2] for glucose, insulin, C-peptide, glucagon GPI and GLP-1.

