The statistical analysis of the oral glucose tolerance curves will be carried out by means of an analysis of variance test for repeated measurements and for the area under the curve of each of the metabolic analytes.

For each of the differences between the area under the initial and final curve of glucose, insulin, C-peptide, glucagon, GPI and GLP-1 between sucralose and water, an ANCOVA will be made, taking the BMI as a covariate.

For the analysis of the behavior of the intestinal microbiota, a comparison of the percentages of the flora between the first and the last sample of excrement will be carried out, and a chi square test will be applied.

The correlation between the initial HOMA-IR value and the glucosylated hemoglobin will be explored.

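### The protocol adjusts the acute AUC comparison for BMI; the SAP, as most naturally read, names no covariate for it, and neither document uses the pre-dose value as one

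*SAP*

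**What the plan says.** **Protocol, Principal outcome.** The outcome is insulin AUC, after both acute and chronic exposure.

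**Protocol, Materials and Methods.** Sucralose or placebo is taken at -15 min and glucose at 0 min, with blood drawn at both times. For acute exposure, mean differences in glucose AUC "between the sucralose groups versus placebo will be compared, adjusting for BMI". A later sentence lists insulin, glucagon, C-peptide, GIP, GLP-1 and the inflammatory markers, "with the purpose of comparing their values in the acute exposure scheme and chronic to sucralose, adjusting for BMI".

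**SAP, analysis paragraphs after the sample size section.** The tolerance curves are to be analysed by a repeated-measures analysis of variance "and for the area under the curve of each of the metabolic analytes". No covariate is given. BMI appears in two other places:

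- The metabolic AUCs: "For each of the differences between the area under the initial and final curve of glucose, insulin, C-peptide, glucagon, GPI and GLP-1", compared between sucralose and water, "an ANCOVA will be made, taking the BMI as a covariate".
- The inflammatory markers, as before/after differences "for the whole sample, adjusting for BMI, these differences will be compared for each analyte related to chronic inflammation".

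The SAP does not mention acute exposure by name.

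**The concern.** Acute exposure is half of the principal outcome, and the two documents, which carry the same date, do not clearly give it the same model. The protocol's model includes BMI. The SAP sentence that most naturally covers the first-test AUC has no covariate. An analyst could defend either version after seeing the data, and prespecification is meant to close off that choice.

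There is also a cost in precision. BMI is already used elsewhere in the SAP, and a pre-dose sample of each metabolic analyte is already drawn. Leaving both out of the acute model forgoes information that needs no further data collection.

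**Working it through.** **1. Which SAP sentence covers the acute comparison?**

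| Comparison | Protocol | SAP, natural reading |
|---|---|---|
| First-test AUC, sucralose vs placebo (acute) | BMI-adjusted: glucose AUC explicitly, insulin and others by the later sentence | Analysis of variance, no covariate named |
| First-to-last AUC change, sucralose vs water | Not set out in this form; final AUC between groups and start-to-end within sucralose, both BMI-adjusted | ANCOVA with BMI |
| Inflammatory markers | BMI-adjusted | Before/after differences, BMI-adjusted |

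The change analysis cannot stand in for the acute one. Let E1 be the sucralose-minus-placebo difference in AUC at the first test and E2 the same difference at the last test. The between-group contrast in change estimates E2 - E1. The acute effect is E1, because the first test follows the dose taken at -15 min. If E1 and E2 were equal, the contrast in change would be zero whatever the size of the acute effect.

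**2. Reproduce the SAP's power.** Inputs from its Estimation of sample size section: d = 0.419231264, n = 72 per group, one-sided alpha 0.05, equal allocation.

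- Noncentrality: d × √(n/2) = 0.419231264 × √36 = 2.5154.
- Degrees of freedom: 2 × 72 - 2 = 142; critical t = 1.6557.
- Power from the noncentral t: 0.8047.

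All of these match the SAP output. The calculation is for an unadjusted t test and takes no credit for a covariate.

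**3. Add baseline adjustment.** Let ρ be the within-group correlation between AUC and the covariate (the multiple correlation if there are two). Residual variance is multiplied by 1 - ρ², so the standardized effect becomes d/√(1 - ρ²) and one degree of freedom is lost. The documents give no ρ, so the range below is an assumption.

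| ρ | 1 - ρ² | d/√(1 - ρ²) | Noncentrality | Power at 72 per group | n per group for 80% |
|---|---|---|---|---|---|
| 0 (unadjusted) | 1 | 0.4192 | 2.5154 | 80.5% | 72 |
| 0.1 | 0.99 | 0.4213 | 2.5281 | 80.8% | 71 |
| 0.2 | 0.96 | 0.4279 | 2.5673 | 81.9% | 69 |
| 0.3 | 0.91 | 0.4395 | 2.6368 | 83.6% | 65 |
| 0.4 | 0.84 | 0.4574 | 2.7445 | 86.1% | 60 |
| 0.5 | 0.75 | 0.4841 | 2.9045 | 89.4% | 54 |

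With a second covariate, losing one more degree of freedom does not change power to the decimal shown. Even at ρ = 0.1 adjustment does not reduce power.

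**4. Which baseline values are eligible?** BMI at entry and the -15 min sample precede any effect of the dose. The 0 min sample is drawn 15 minutes after it and is post-exposure. No pre-exposure AUC exists.

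**The case against.** **The SAP may not contradict the protocol.** The ANCOVA sentence is loosely worded. It could be read as covering sucralose-versus-water differences in the initial AUC and in the final AUC separately, each adjusted for BMI, which would agree with the protocol. The SAP also never says that the acute comparison is unadjusted. This has some force: a reader might infer a deliberate switch to an unadjusted analysis, and the text does not establish that. But the change reading is the more natural one, and a principal analysis should not hang on the choice.

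**The explicit acute AUC sentence in the protocol is about glucose.** Correct. For insulin, the adjustment rests on the later sentence, which refers to circulating levels and not to AUC. That sentence does name the acute scheme and BMI, so the intention is reasonably clear.

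**Fasting insulin is not ignored.** A reader might infer that neither document uses it at all. That goes too far: the SAP explores the correlation of initial HOMA-IR, an index built from fasting insulin and glucose, with glycosylated hemoglobin. What stands is that no analysis names the -15 min value as a covariate. Its absence is a missed refinement and is not part of the disagreement between the documents.

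**The -15 min value may be part of the outcome.** The documents do not say whether AUC is total or incremental, or whether it starts at -15 or 0 min. If it starts at -15 min, the covariate is one component of the AUC; if it is incremental, a baseline has already been subtracted. Either affects how much the covariate explains. Neither invalidates ANCOVA, because the value is fixed before the dose can act.

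**Conclusion.** The point holds as a gap in specification and a loss of precision. The protocol adjusts the acute comparison for BMI, and the SAP does not clearly carry that over to the first-test AUC.

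It should not be read as a claim of bias. A reader might infer that chance imbalance in BMI or fasting insulin would invalidate the unadjusted result. Randomization keeps that comparison valid, and the SAP also plans a descriptive check of balance.

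The size is modest and uncertain. Power rises from 80.5% to 80.8%–83.6% for a correlation of 0.1 to 0.3, and to 86.1%–89.4% for 0.4 to 0.5. A reader might infer a gain to 84%–91% by supposing that BMI and -15 min insulin together explain 10% to 30% of AUC variance. The documents support no such figure, and neither promises the second covariate. The effect of restoring BMI alone could lie at the bottom of the range.

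All figures use the SAP's own two-group calculation. The protocol describes two sucralose doses and placebo, so they apply to a given dose contrast only if each of its groups has 72 participants.

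**What to change.** Add to the SAP, for example: *The insulin AUC of the first oral glucose tolerance test is compared between each sucralose group and placebo by ANCOVA, with baseline BMI and the -15 min insulin value as prespecified covariates; this is the principal acute analysis. The first-test AUC of each other metabolic analyte is analysed in the same way, with that analyte's own -15 min value.*

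State also that the 0 min value is not used as a covariate because it is post-dose, and say how AUC is defined (start time; total or incremental). If the sponsor prefers to restore BMI alone, that settles the disagreement with the protocol and leaves only the refinement undone.

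The cost is SAP wording and one degree of freedom for BMI alone, or two with the -15 min value. No additional samples, visits or participants are needed.

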Furthermore, it has not been studied until now whether the acute or prolonged consume of NCS such as sucralose is capable to cause a systemic inflammatory state and if this is related to the development of glucose intolerance in healthy individuals. This has generated in the scientific community a polemical discussion about the possible association between the consume of sweeteners and the development of glucose intolerance; which is characterized by the elevation in the AUC of insulin, glucose, C peptide, glucagon, GIP and GLP-1, as well as the rise of systemic inflammatory factors. Whence the aim of this research was measure the effect of the acute and chronic exposure to sucralose on blood glucose, insulin, C-peptide, GIP and GLP-1 levels and the reduction of interleukins 4, 10, 13 in young and healthy adults.

Relevance of the study

Until now, the international agencies safety assessment of non-caloric sweeteners has been enough to recommend their use in humans. This confidence has led to a mass production and use of these additives for the western population of all ages, complemented by the absence of epidemiological evidence focused on trade

adversities to the consumption of these substances. However, recent studies have revealed some studies that relate a state of glucose intolerance and insulin resistance with the chronic consumption of some of these available in the market products, as in the case of sucralose. Unfortunately, the results of these studies have been criticized for the lack of methodology robustness used and for omitting the presence of other markers that are directly involved with metabolic dysfunctions; the only consideration was the symptom of sucralose on the intestinal microbiota. Therefore, it is necessary to determine if the acute or chronic consumption of sucralose is capable of inducing a glucose intolerance and insulin resistance state in humans, through the performance of a dependable robust prospective, randomized, double blind study and placebo controlled, which allows us to issue reliable recommendations on the habitual use of non-caloric sweeteners in our population.

Hypothesis

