In healthy, young volunteers, subjected to an oral glucose tolerance curve of 180 minutes, acute or chronic exposure to 48 - 96 mg of sucralose in a single dose or 10 weeks daily intake, respectively, causes an increase in the average levels of the area under the curve of insulin, glucose and other intolerance to this carbohydrate markers when compared with water as a placebo.

Principal outcome

To evaluate the effect of acute and chronic exposure to 48 - 96 mg of sucralose in a single dose or for 10 weeks, respectively, on the average levels of the area under

the insulin curve in healthy, young volunteers, subjected to an oral glucose tolerance curve at 180 minutes, in a randomized, double-blind, placebo-controlled study.

Materials and Methods

This is a randomized, double-blind, placebo-controlled trial in young and healthy adults, the study at the General Hospital of Mexico, [name] from April 2016 to June 2018, and the present study meets with the criteria of CONSORT.

To evaluate the acute effect of sucralose, the experimental groups will receive 48 mg / 60 ml and 96 mg / 60 ml of fasting sucralose in a single shot, while the control group will receive 60 ml of water as a placebo, before undergoing a CTOG with 75 g of glucose during 180 min. During this procedure, 4 ml of blood will be taken at -15 (sucralose intake or placebo) and 0 (75 g glucose intake) as a base and then at 15, 30, 45, 60, 75, 90, 105, 120 and 180 minutes post-load glucose for the quantification of insulin, glucose, C-peptide, glucagon, GLP-1, and GPI levels. Subsequently, to evaluate the chronic effect of sucralose, the experimental group will continue with the daily intake of 48 – 96 mg / 60ml of sucralose for 10 consecutive weeks, while the control group will receive 30 ml of water daily as a placebo during the same period of time. At the end of 10 weeks of treatment with sucralose or placebo, a second CTOG (75g / 180 min) will be carried out, taking again 4 ml of blood at -15 and time zero, and subsequently 4 ml at 15, 30, 45, 60, 75, 90, 105, 120 and 180 minutes after glucose loading. To evaluate the acute exposure to the sweetener, the area under the curve (AUC) of the blood glucose levels obtained during the CTOG in each participant will be calculated and the average differences

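### The SAP does not carry the protocol's principal outcome, insulin AUC, into its analysis: six analyte AUCs get the same unadjusted test, and the hypothesis could rest on any one of them

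*SAP*

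**What the plan says.** **Where insulin comes first.** Under Principal outcome, the protocol sets out to evaluate the AUC of "the insulin curve in healthy, young volunteers, subjected to an oral glucose tolerance curve at 180 minutes". The SAP's Estimation of sample size rests on "the difference of the averages of the areas under the curve for plasma insulin in obese volunteers exposed to sucralose and water". The title of both documents names serum insulin.

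**Where that priority is missing.**
- Protocol, Hypothesis: sucralose "causes an increase in the average levels of the area under the curve of insulin, glucose and other intolerance to this carbohydrate markers". The list is open-ended, and nothing says how many markers must rise.
- Protocol, Materials and Methods: the acute effect is to be judged by comparing the AUC of blood glucose between the sucralose groups and placebo. Insulin then appears among the additional measurements.
- SAP, paragraph on the oral glucose tolerance curves: repeated-measures analysis of variance, "and for the area under the curve of each of the metabolic analytes".
- SAP, ANCOVA paragraph: sucralose against water with BMI as covariate, "For each of the differences between the area under the initial and final curve of glucose, insulin, C-peptide, glucagon, GPI and GLP-1". Insulin is second in a list of six that are treated alike.

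**Error rate.** The only alpha stands in the sample-size section, for a one-sided t test: "with an alpha value (0.05), assuming unequal variances, for a power of proof of 80" percent. For the ANCOVAs the SAP states no alpha, sidedness, multiplicity adjustment or testing order.

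**The concern.** The protocol wants a trial robust enough to support recommendations on habitual sweetener use, and its question is whether sucralose induces glucose intolerance. Read with the hypothesis, the SAP lets that question be answered by whichever of six AUCs turns out raised. Suppose insulin AUC shows no difference but GLP-1 or C-peptide AUC is nominally significant. One reader would say that the principal outcome failed. Another could say that a marker of intolerance rose, as the hypothesis predicted. Nothing in the SAP settles which is right, so the rule could be chosen after the results are known. The false-positive rate of a conclusion reached by the second route is not 5%.

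**Working it through.** **1. The plan's own figure.** Inputs from the SAP's Estimation of sample size: d = 0.419231264, 72 per group, one-sided alpha 0.05.
- Noncentrality = d × √(72/2) = 0.419231264 × 6 = 2.5154.
- Critical t with 142 degrees of freedom = 1.6557.
- Power from the noncentral t distribution = 0.8047.

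All three agree with the SAP. The stated power is therefore for one one-sided test on one AUC, insulin.

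**2. Inputs for the error rate.**
- Number of tests: k = 6 (SAP, ANCOVA paragraph).
- Alpha per test: 0.05. This is an inference, because the value appears only in the sample-size section.
- Sidedness: not stated for the ANCOVAs, so both cases are shown.
- Correlation ρ between the six test statistics: not in the documents. A common value is assumed and varied from 0 to 0.8.
- Scope: one exposure and one sucralose-versus-water contrast.

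**3. Formula.** The hypothesis claims an increase, so only rejections in the upward direction count. If sucralose has no effect on any analyte,

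P(at least one false increase) = 1 − ∫ φ(u) · [Φ((c − √ρ·u)/√(1 − ρ))]^k du,

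with c = 1.645 for one-sided 0.05 and c = 1.960 for the upper tail of a two-sided 0.05 test. At ρ = 0 this reduces to:
- one-sided: 1 − 0.95^6 = 26.5%;
- two-sided, upward only: 1 − 0.975^6 = 14.1%.

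**4. Results for six AUCs.**

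| Assumed ρ | One-sided 0.05 | Two-sided 0.05, increases only |
|---|---|---|
| 0 | 26.5% | 14.1% |
| 0.3 | 22.0% | 12.2% |
| 0.5 | 18.6% | 10.4% |
| 0.7 | 14.8% | 8.2% |
| 0.8 | 12.6% | 6.9% |

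Against the 5% of a single one-sided test, the one-sided column is 2.5 to 5.3 times as large (12.6/5 and 26.5/5), and 3.7 times at ρ = 0.5. Against the 2.5% upward error of a single two-sided test, the last column is 2.8 to 5.6 times as large (6.9/2.5 and 14.1/2.5).

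**5. The five AUCs other than insulin.** At ρ = 0.5 the same formula with k = 5 gives 16.6% one-sided. Most of the excess thus comes from the analytes that have no stated status.

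**6. What the remedies do to power for insulin.** With insulin as the only confirmatory test, the 80.5% above is kept. Six co-equal tests with Bonferroni (0.05/6 = 0.0083, one-sided) would reduce it to 53.8% at 72 per group.

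**The case against.** The strongest reply is that the outcome is already ranked. Insulin AUC stands alone under Principal outcome, is the basis of the sample size and is in the title. A conclusion drawn from insulin AUC alone, on one contrast, carries the nominal error, and the proposed change largely restates the protocol. This stands as far as it goes. A reader might infer from the SAP's list that no outcome has been given priority at all; the protocol does not support that. The gap is confined to the SAP's analysis text and the five other AUCs. It still matters because the hypothesis is wider than insulin and because the methods put glucose first for the acute comparison.

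Three other readings also go too far.
- **The size.** At a correlation of 0.5, six two-sided tests give at least one rejection in either direction in 20.7% of null trials. A reader might take that as the chance of a false intolerance marker. It counts false decreases too, which cannot support a claimed increase; the matching figure is 10.4%.
- **Power.** A reader might take the hypothesis to require all six AUCs to rise, and conclude that the stated 80% fails. No passage states such a rule, and the effect size was derived for insulin only, so no joint power can be computed from the documents.
- **The Background.** The sentence that calls glucose intolerance something "which is characterized by the elevation in the AUC of insulin, glucose, C peptide, glucagon, GIP and GLP-1" goes on to add inflammatory factors. It describes a scientific debate and is not a decision rule.

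**Conclusion.** The concern holds in a limited form. Insulin AUC is the principal outcome, but the SAP does not say that it decides the metabolic question, and it gives the other five AUCs identical unadjusted tests with no status. If any raised marker may count, the chance of at least one false increase on a single contrast is about 13% to 26% with one-sided tests, or about 7% to 14% with two-sided tests.

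These figures rest on three assumptions: 0.05 for each ANCOVA, a common correlation between 0 and 0.8, and no true effect on any analyte. They leave out the two doses, the acute and chronic comparisons and the inflammation panel. This should be corrected, but it does not invalidate a conclusion drawn from insulin AUC alone on one prespecified contrast.

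**What to change.** 1. State in the SAP that insulin AUC is the only confirmatory metabolic test, at the stated alpha, and state its sidedness. Name the contrast: which exposure, and which sucralose group or groups against water. Without that, naming insulin alone does not hold the error at 5%.
2. Reword the hypothesis so that its confirmatory claim concerns insulin AUC, and align the acute-comparison text in Materials and Methods, which now refers to glucose AUC.
3. Give the AUCs of glucose, C-peptide, glucagon, GIP and GLP-1 a stated status. Either make them secondary, tested only if insulin AUC is significant and Holm-adjusted across the five, or make them exploratory, with estimates and confidence intervals and no confirmatory claim. Either choice is adequate.

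The cost is wording only: no further volunteers, samples or assays, and no loss of the power stated for insulin. The one small downside is that a lone nominally significant marker other than insulin could no longer be presented as proof of glucose intolerance.

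### The microbiota analysis applies a chi-square test to first-versus-last stool percentages without stating the counting unit, the pairing or a contrast with water; if the percentage is relative abundance, it is the wrong test

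*SAP*

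**What the plan says.** The SAP gives the microbiota one sentence, near its end: a comparison of "percentages of the flora between the first and the last sample of excrement will be carried out, and a chi square test" is to be applied.

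Materials and Methods in the protocol adds the assay and little else. "The samples of excrement from acute and chronic exposure will be processed to extract the DNA", real-time PCR is run, and "the percentage of each bacteria present in feces will be compared at the beginning and at the end". Then: "The difference between the two samples will be analyzed by means of square chi".

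Neither document gives a denominator for the percentage, says how the two samples from one person are linked, or names a comparison between arms for this outcome.

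Other outcomes are treated differently. For the inflammatory markers the SAP specifies "comparing the before / after differences between the sucralose and water groups for the whole sample, adjusting for BMI". For the initial-to-final AUC differences it specifies an ANCOVA of sucralose against water with BMI as covariate.

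**The concern.** A chi-square test needs a table of counts of independent units. A percentage of each bacterium in a stool sample, obtained by real-time PCR, reads most naturally as relative abundance. That is a continuous quantity measured twice in each participant. It provides no count table, and the two measurements are not independent. To run the test, an analyst would have to choose a denominator, and that choice would decide the p-value.

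The percentage could, less naturally, be the share of participants in whom a bacterium is found. The unit is then a person and a chi-square-type test is possible, but the plan does not say whether it is the paired form (McNemar) or the unpaired form.

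On both readings the only contrast named is last sample against first. Taken alone, it cannot separate an effect of sucralose from a change over ten weeks that is common to all arms. At stake is whether the microbiota results can be interpreted at all.

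**Working it through.** **The plan's own figure.** The documents give no figure for the microbiota. The only sizing is for insulin AUC (SAP, Estimation of sample size): d = 0.419231264, one-sided alpha 0.05, 72 per group. It reproduces: noncentrality = d × √(72/2) = 0.419231264 × 6 = 2.5154, df 142, critical t 1.6557, power 0.8047. Nothing below depends on it or changes it.

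**Relative abundance: dependence on the denominator.** All inputs are assumed. Take 40% in the first sample, 45% in the last, and N units per sample. The uncorrected chi-square is

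χ² = (p₂ − p₁)² / [p̄(1 − p̄) × 2/N], with p̄ = 0.425,

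so χ² = N × 0.0025 / (2 × 0.425 × 0.575) = N × 0.005115.

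| N per sample | χ² | p |
|---|---|---|
| 72 | 0.368 | 0.54 |
| 100 | 0.511 | 0.47 |
| 1,000 | 5.115 | 0.024 |
| 7,200 (72 × 100) | 36.83 | 1.3 × 10⁻⁹ |

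The result crosses 0.05 at 3.8415 / 0.005115, that is, from N = 752. The number 72 appears in the SAP, but as participants per group; it is not a stool counting unit. The pattern does not depend on the percentages chosen: 20% against 25% gives p = 0.40 out of 100 and 0.007 out of 1,000.

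**Relative abundance: type I error.** This was simulated with assumed inputs: 72 pairs, share around 20%, no true change, between-person SD 0.8 and within-person SD 0.3 to 0.8 on the logit scale, nominal two-sided 0.05.

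| Analysis | Type I error |
|---|---|
| Paired t-test | 0.04 to 0.06 |
| Chi-square, mean percentages taken out of 100 | about 0 |
| Chi-square, pooled, 100 counts per sample | 0.10 to 0.51 |
| Chi-square, pooled, 1,000 counts per sample | 0.61 to 0.83 |

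The error can go in either direction, according to a choice that the plan does not make.

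**Presence/absence: paired or unpaired.** With within-person correlation φ, an unpaired chi-square at nominal 5% has a true type I error of about P(|Z| > 1.96/√(1 − φ)): 1.9% at φ = 0.3, 0.6% at 0.5 and 0.03% at 0.7. It is conservative.

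As an assumed example, take 30 of 72 carriers at first and 38 of 72 at last. The unpaired test gives χ² = 1.783, p = 0.18. McNemar's test depends on how the net gain of 8 arises:

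| Gained / lost | Exact McNemar p |
|---|---|
| 10 / 2 | 0.039 |
| 14 / 6 | 0.115 |
| 18 / 10 | 0.185 |

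The loss from ignoring pairing can therefore be large or negligible. It is greatest when carriage is stable within a person.

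**Contrast with water.** Suppose water also moves from 40% to 45%. The sucralose-minus-water difference is 5 − 5 = 0 percentage points, yet the out-of-1,000 test in the sucralose arm alone still gives p = 0.024.

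**The case against.** Several points can be made for the plan, and most of them narrow the concern.

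- *A chi-square test does not mean an unpaired one.* McNemar's test is itself a chi-square test. This stands for the presence/absence reading: there the supportable criticism is that the pairing is unspecified, not that the plan chose an unpaired test. It does not help the abundance reading, where there are no counts to pair.
- *A reader might infer that a drift common to all arms will be reported as a sucralose effect.* The documents do not support that. They do not restrict the first-versus-last comparison to the sucralose arms. If it is run and reported in every arm, a common drift would show under water too. Even then, setting within-arm p-values side by side is not a test of the difference between arms.
- *A reader might infer that water-arm stool is not collected, or that the first sample follows a sucralose dose.* Neither is stated. The protocol refers to samples from acute and chronic exposure, but also to the beginning and the end, and the SAP to a first and a last sample. Whether the beginning precedes the first intake is left open.
- *The figures are illustrations.* This is true: every microbiota input is assumed. They show that the result is undefined without a unit; they do not predict the trial's result.
- *The outcome is minor.* The microbiota is absent from the stated aim, the Hypothesis and the Principal outcome. The Background cites an animal study that attributed its finding to the microbiota. The remark in Relevance of the study that in earlier work "the only consideration was the symptom of sucralose on the intestinal microbiota" is a criticism of that work's narrowness, and so is weak evidence that the outcome matters here.

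**Conclusion.** The concern holds in a limited form. That the unit, the pairing and the water contrast are all unstated follows from the text alone. That chi-square is the wrong test depends on reading the percentage as relative abundance, which the wording and the assay favour but do not settle. On that reading the same data can give a null or a significant result (0.47 or 0.024 in the assumed example) according to an arbitrary denominator. On the presence/absence reading the defect is smaller: an unspecified pairing, with loss of power if the unpaired test is used.

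A reader might go further and conclude that the plan rules out a comparison with water, or that the trial's main conclusion is at risk. Neither follows. The contrast is unstated, not excluded, and the insulin AUC result and the sample size are untouched. The change should be made, but it concerns a secondary analysis.

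**What to change.** In both the SAP and Materials and Methods:

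1. State the unit: relative abundance per participant, or presence/absence per participant.
2. Replace the chi-square test with a comparison of sucralose and water for each bacterium.
   - For relative abundance: an ANCOVA on suitably transformed last-sample abundance, with first-sample abundance and BMI as covariates. This is close to the SAP's existing approach to the AUCs.
   - For presence/absence: a logistic model of last-sample presence adjusted for first-sample presence, with McNemar's test kept for within-arm description only.
3. Say how multiplicity across bacteria is handled, or label these results exploratory.
4. Confirm that stool is collected in the water arm and that the beginning sample precedes the first sucralose intake. If it does not, that sample cannot be treated as an unexposed baseline.

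The cost is revised wording and a little more analysis, provided that water-arm stool is already collected. If it is not, water-arm samples and assays would have to be added.
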